8.3 Intervening on "Social Harms"

Focus groups, interviews, and surveys will contain questions regarding stigma and other personal experiences, and some participants may be uncomfortable answering certain questions. Social, psychological, and interpersonal harms may include being discriminated, feeling stigmatized, emotional distress, as well as feelings of discomfort and embarrassment. Additionally, this study involves provision of home HIV/STI testing which may cause participants to worry or become anxious. If the HIV/STI test results are reactive (e.g., a "preliminary positive" on the HIV rapid antibody test), participants may become depressed or feel anxious.

All study sites have specific policies governing the treatment of human subjects. These policies specify that medical and psychological assistance will be available in the immediate environment in the event a participant should experience any adverse reactions resulting from study procedures.

While participants will be informed that they may refuse to answer any question at any time, responses or reactions to certain questions may indicate distress on the part of the participants. Participants experiencing mild distress during a study visit will be offered a small break or to reschedule the interview at a later date. In the unlikely event that a participant experiences considerable distress they will be offered a voluntary clinical assessment and/or counseling on site. Study staff will be trained to make appropriate referrals for clinical care in consultation with the PIs or designee to help participants cope with any feelings and/or questions they have which may arise.

If at any time during the study, a participant divulges that he is at risk for harm, including but not limited to being abused or experiencing violence, if harm is suspected or likely, or if the participant states he is suicidal/homicidal, measures will be taken to ensure his safety. Reporting will be done as appropriate to the situation and the legal statutes, including reporting to child protection agencies or other appropriate agencies and referrals will be provided to appropriate support, counseling, or treatment resources.

9.0 MONITORING UNTOWARD EFFECTS ASSOCIATED WITH OR RESULTING FROM STUDY

Site research staff must first follow their own IRB's procedure for reporting and managing untoward effects.

There are two types of untoward effects to be identified: (1) those related to the participant, and (2) those related to the study staff.

First, the study will catalogue any untoward effect related to the participant as a result of study participation, including use of the LYNX app and home HIV/STI testing. Reporting is required for occurrences including social harms, psychological distress, and serious life threatening events such as suicide attempts. These may be immediately apparent to the study staff, such as the participant's emotional upset requiring referral for counseling; or they may be delayed and reported later to study staff, such as physical harm to an individual for having participated in the study. Study staff will notify the protocol team of these untoward effects using the iTech QNS accessible through the iTech website (www.itechnetwork.org). Study staff will be briefed during the training on the scope of possible untoward

effects and instructed to report events.

Second, study staff may encounter untoward events during sessions that personally affect them. Training and guidance will seek to minimize this risk. Nonetheless, an assessment of the cost of conducting this study must include cataloguing these events as well. The protocol chairs should be notified of these events so that they may be immediately addressed, evaluated, and guidance modified or expanded to minimize similar risk to other study staff.

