5.4.3.4 Study Follow-up

All enrolled participants will be followed for 24 weeks. After enrollment, all follow-up visits will occur online, with SMS reminders, email, and phone follow-up conducted as needed to ensure completion of study procedures. Participants will complete an online CASI at 12 and 24 weeks and receive a stipend for completion of procedures at each study visit. Visit windows will be approximately 14 days before/after the target date. Participants will also be able to obtain additional home HIV self-test kits during the study follow-up, if needed. At the 3 month visit, any persons who have a positive HIV test plus up to 20 participants randomized to the LYNX arm will participate in an in-depth interview conducted by UCSF/SFDPH study staff via video-conferencing. The purpose of this interview is to elicit feedback on their experiences using the app, any technical difficulties encountered, and how the app could be further improved. Participants will be selected for interviews using purposive sampling based on level of engagement with the app, whether participants completed HIV/STI testing and/or initiated PrEP during the study, and to achieve diversity based on sociodemographics (e.g. age, race/ethnicity). Additionally, we will offer interviews to all participants who have a confirmed HIV diagnosis. In addition to asking about their experiences using the app, these participants will also be asked about additional information or support that would have been helpful at the time of receiving a positive HIV test result, and their experiences in getting linked to HIV care. By purposively sampling certain participants for the exit interviews, the goal is to select "information-rich cases from which one can learn a great deal about issues of central importance to the purpose of the research."⁵¹ All interviews will be audio recorded for transcription and analysis. Participants will be reimbursed for completion of each study visit according to local study site guidelines.

We will also conduct medical record abstraction for participants in this study. The goal of the medical record abstraction is to explore whether it is feasible to collect more objective measures of HIV and STI

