7.3 Data Collection

7.3.1 CRFs

Study monitoring data, including information about eligibility, demographic data, and monitoring untoward effects, will be collected on CRFs. All CRFs for this study will be available for download from a secure iTech Box account. Hard copies of CRFs may be ordered from the MC via an order form on

the iTech website.

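### No scheduled enquiry about harm from taking part, identical in both arms, is described, so recorded untoward effects may be incomplete and may not be comparable between arms

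*Combined protocol and SAP*

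**What the plan says.** Section 9.0 sets a wide scope: "the study will catalogue any untoward effect related to the participant as a result of study participation", including effects of app use and of home testing. It describes two ways an effect comes to light. In the first, "These may be immediately apparent to the study staff"; otherwise, "or they may be delayed and reported later to study staff, such as physical harm to an individual". Staff then notify the protocol team through the network's query and notification system (QNS). Section 7.3.1 gives the place of record: "Study monitoring data, including information about eligibility, demographic data, and monitoring untoward effects, will be collected on CRFs".

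Section 5.4.3.4 sets the follow-up for the pilot RCT: "All enrolled participants will be followed for 24 weeks", and "After enrollment, all follow-up visits will occur online, with SMS reminders, email, and phone follow-up conducted as needed". The scheduled assessments in both arms are self-administered online surveys (CASI) at weeks 12 and 24. A video interview at month 3 is planned for as many as 20 LYNX participants, plus anyone in either arm with a positive HIV test. Its stated purpose is feedback on the app.

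Section 6.3.3 lists the on-study measures. Anxiety, depressive symptoms, abuse and trauma are among them, at baseline and follow-up and without restriction by arm, as potential moderators of the intervention. No listed item asks whether taking part caused a problem.

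**The concern.** The promise in section 9.0 and the data collection in sections 5.4.3.4 and 6.3.3 do not meet. An effect is apparent to staff only if staff are in contact with the participant, and after enrollment contact is mostly remote and self-administered. An effect reported later depends on the participant raising it, because no question, form or time point is named that would prompt him.

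This matters more here than in most app pilots. Section 4.4 justifies waiving parental permission partly by the danger that a minor is outed. Home kits sent by mail and reminders on a phone (section 5.4.3.2) are ways in which the study itself could contribute to disclosure. Without a solicited question, a report of no social harms cannot be told apart from nobody having been asked. These exposures also sit mainly in the LYNX arm, which has the interviews too, so an excess of recorded events in LYNX could reflect exposure, contact or both.

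**Working it through.** The documents give no harm rate, detection probability or harms sample size, so there is no stated figure to reproduce. The check has three parts.

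**1. Opportunity for live contact, by arm**

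| After enrollment | LYNX (N=40) | Control (N=20) | Source |
|---|---|---|---|
| Online CASI, weeks 12 and 24 | all | all | 5.4.3.4 |
| Routine month-3 interview | up to 20/40 = 50% | 0/20 = 0% | 5.3, 5.4.3.4 |
| Interview after a positive HIV test | yes | yes | 5.4.3.4 |
| Phone call after a positive home specimen | yes | yes | 6.4 |
| Pre-visit contact; optional survey completion at the site | yes | yes | 8.1, 8.2 |
| Premature-discontinuation visit | yes | yes | 6.3.4 |
| Listed question on harm from taking part | none | none | 6.3.3 |

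Only the routine interview differs by design. None of these contacts is described as asking about harm.

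**2. What unequal contact could do (illustration; s and q are assumptions)**

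Give both arms the same true harm rate. Let s be the probability that a harm reaches staff unprompted, and q the probability that an interview surfaces it. With 20 of 40 LYNX participants interviewed:

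- control captured share = s
- LYNX captured share = 0.5·s + 0.5·[1 − (1 − s)(1 − q)]

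| s | q | Control | LYNX | Ratio |
|---|---|---|---|---|
| any | 0 | s | s | 1.0 |
| 0.5 | 0.5 | 0.50 | 0.625 | 1.25 |
| 0.5 | 0.8 | 0.50 | 0.70 | 1.4 |
| 0.2 | 0.8 | 0.20 | 0.52 | 2.6 |
| 0.1 | 0.8 | 0.10 | 0.46 | 4.6 |

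For example, take a true rate of 10% with s = 0.2 and q = 0.8. Control has 20 × 0.10 = 2 events, of which 2 × 0.2 = 0.4 are expected on record. LYNX has 40 × 0.10 = 4 events, of which 4 × 0.52 = 2.1 are expected.

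**3. What a count of zero would mean**

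If all n participants are asked, all answer, and none reports harm, the one-sided 95% upper bound is 1 − 0.05^(1/n):

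- LYNX, n = 40: 7.2%; after 20% attrition (the upper end of the range in section 10.1.3), n = 32: 8.9%
- Control, n = 20: 13.9%; after 20% attrition, n = 16: 17.1%

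If only a fraction c of events reaches the record, the bound on the true rate becomes about 7.2%/c for n = 40. That is 14% at c = 0.5, 29% at c = 0.25 and 72% at c = 0.10. These values of c are assumed and show only how the bound moves.

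**The case against.** The best case for the plan has four parts.

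*The surveys are not silent.* Mood, trauma and abuse are measured repeatedly in both arms (6.3.3), and section 8.3 says surveys ask about stigma. A reader might infer that harm detection is wholly spontaneous; the documents do not support that. But these answers are not attributed to participation, and no rule carries them to the untoward-effects record.

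*Staff contact exists in both arms.* The table lists it, and the discontinuation visit covers people who may be leaving because of a harm. This stands, but no harms enquiry is described at any of these contacts. Section 11.3.1 also says that all data collection takes place in supervised clinical settings. That does not agree with online follow-up in 5.4.3.4 and should be reconciled.

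*The question may exist elsewhere.* Section 6.0 calls its lists a summary, the survey instruments are not in the document, section 9.0 puts site IRB procedures first, and section 11.3.1 mentions a data and safety monitoring plan without describing it. This is fair: the finding is that no such enquiry is described, not that none exists.

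*Disclosure is mitigated.* Reminders are nonspecific (5.4.3.2), push notifications in the study management app are generic (7.4.3), and contact messages do not reveal the nature of the study (11.3.1). These steps lower the risk, but nothing described measures whether they worked.

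**Conclusion.** The gap holds in a limited form. The protocol promises a full catalogue of participation-related harm and describes no scheduled, arm-neutral enquiry that would supply it. Recorded harms may be incomplete and may not be comparable between arms. The primary endpoints, usability score and app opening, are unaffected.

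Two stronger readings are tempting and should be resisted. First, a reader might infer that harms will in fact be under-counted more in control. Only the opportunity for contact is known to differ, 50% against 0%. If the app-feedback interview surfaces no harms, the capture ratio is 1.0, and every larger ratio above comes from assumed s and q. Second, a reader might infer that the decision to start the efficacy trial rests on the harms count. Section 1.1 ties that step to feasibility and acceptability, section 10.1.3 sets the criteria for those two, and no comparison of harms by arm is planned.

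The bounds of 14%, 29% and 72% likewise depend on assumed capture and are not estimates for this study.

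**What to change.** Add one item to the week-12 and week-24 CASI, worded identically in both arms: a yes/no question, with free text, on whether taking part (app, kits, messages or surveys) has caused any problem since the last survey, such as disclosure of private information, conflict, threats or harm. The discontinuation visit repeats week-24 procedures as appropriate (6.3.4), so the item should be stated to apply there too.

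In section 9.0, state that any positive answer is passed to site staff, who complete the existing untoward-effect case report form and QNS report. Report solicited and unsolicited events separately, by arm. Under equal true rates, the enquiry itself would then no longer favour one arm by design.

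The cost is one survey item and short additions to 6.3.3 and 9.0, with no new visits. More minor events will be recorded. Free-text answers, some from minors, need timely review by existing staff because they may engage the duties in section 8.3. Section 7.3.3 describes only regular download of survey data, so the route and timing of the hand-over to sites must be written down. The modification goes to the IRB of record under section 11.4.

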10.0 STATISTICAL/ANALYTIC CONSIDERATIONS

10.1 Statistical Analysis Plan

10.1.1 Formative Phase (Aim 1)

FGs and IDIs will be conducted in person or remotely using VSee app or Zoom (or other HIPAA-compliant, IRB approved video- conferencing app). The initial FGs will be facilitated by UCSF/SFDPH study staff in person at the iTech sites in Tampa and Chicago. In person IDIs by UCSF/SFDPH study staff may also be conducted during the site visit, schedules and time permitting. Subsequent FGs and IDIs will be conducted using the VSee app to maximize the flexibility of the data collection in the context of iterative app development. If possible, members of the LYNX design and development team may also participate in the follow-up FGs and IDIs to probe about specific features and app preferences. The FGs and IDIs will be video- recorded to capture YMSM feedback and allow ability to distinguish different speakers. Video also provides important contextual information on participant reactions when viewing and commenting on specific features of the app interface. After each interview, a short debriefing form will be completed by the interviewer noting salient comments on usability of existing features, requested features from the interview, and the overall usefulness of the information obtained for iterative design of the app. These debrief forms will serve as a summary of the interviews and will guide the researchers on what videos or parts of the videos to transcribe and/or review for the app developers. The goal of the analysis will be to evaluate the overall relevance of the app to YMSM and identify ways to adapt specific features of the app to promote STI testing, PrEP uptake, and PrEP adherence among YMSM. The team will meet weekly to discuss emerging findings and whether changes to the interview guide are necessary. Data from these focus groups and IDIs will be used to iteratively refine the app, intervention protocol, and assessment tools prior to the technical pilot in Aim 2.

10.1.2 Technical Pilot (Aim 2)

All exit interviews from the technical pilot will be transcribed in full. Qualitative data will be analyzed by iTech Analytic Core staff using the methods described in aim 1 and will inform efforts to further refine the app, intervention protocol, and assessment tools prior to the launch of the RCT pilot. Quantitative data will be used to characterize participants in the technical pilot and provide further information on the usability of the app.

10.1.3 Pilot RCT (Aim 3)

Response rates to follow-up surveys will be tabulated by recruitment venue and respondent characteristics to help understand potential sources of bias. We will characterize the study population using descriptive statistics and compare the intervention and control groups at baseline using t-, Wilcoxon, and chi-square tests. Point estimates for mean SUS score ≥ 50 and for proportion accessing the app >0.60 will be considered the minimum criteria for acceptability and feasibility, consistent with industry standards.^{49,50} A secondary feasibility outcome will be achieved if $\geq 50\%$ of participants who open the app complete their personalized risk score at least once.

The secondary outcomes of preliminary efficacy of the LYNX app to increase HIV/STI testing (any testing over follow-up) and PrEP uptake (as described above) will be evaluated using unadjusted risk ratios for each outcome. If there is evidence of divergence from balance in measured baseline covariates (i.e., failure of randomization), post-hoc analyses using Poisson regression with robust standard errors will be used to estimate adjusted risk ratios. Outcome variables will represent any HIV testing and any PrEP uptake over the follow-up period. Separate models will be estimated for each outcome.⁵²

With 60 participants randomized 2:1 to intervention: control, and 10-20% attrition, we will have 80% power to detect 37-42 percentage point increases in HIV testing and PrEP uptake, depending on rates in controls. The lack of precision and large minimum detectable effects, typical of pilot studies, will entail careful interpretation of study results in the light of overall patterns, plausibility, and findings from other mHealth studies.

Qualitative data from exit interviews will be analyzed by the LYNX team using the methods described in Aim 1 and will inform efforts to finalize app revisions and prepare for efficacy evaluation of the app.

Note: Any deviations from the analysis plans outlined above or in the sections that follow will be documented and justified in the Statistical Analysis Plan developed for this protocol.

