Pre-Exposure Prophylaxis (PrEP) has demonstrated high efficacy, but uptake has been low among YMSM. The iPrEx trial, in which half the participants were under 25, demonstrated an estimated >90% PrEP efficacy among MSM with detectable drug levels in blood.^{28,29} Despite these results, there have been myriad challenges to increasing PrEP uptake in the US, including low awareness, concerns about side effects, low risk perception, and PrEP stigma.³⁰⁻³³ According to national prescription data, youth under 24 are the least likely to initiate PrEP, with only 9% of PrEP initiations in 2015 occurring in this age group.³⁴ In a recent national survey, only half of YMSM aged 15-24 had heard of PrEP, and 1.7% had ever used PrEP.³⁵ Demonstration projects also highlight challenges with PrEP uptake. In the US Demo Project of 550 MSM, only 20% were age 25 or under, and PrEP uptake was lower among younger, non-white, and less educated persons. Self-perceived risk was low among those declining PrEP, despite high rates of condomless sex and STIs in this group.³⁶ In the ATN 110 study of YMSM aged 18-22, PrEP uptake was only 16%, and PrEP adherence was lower among Black YMSM and declined overall during follow-up, particularly with less frequent visits.³⁷ Taken together, these data point to deficits in self-perceived risk which may result in low PrEP uptake, especially among YMSM of color, and the importance of engaging youth when offering and delivering PrEP.

Mobile technologies have enormous potential to reach and engage YMSM in HIV prevention.³⁸⁻⁴² Mobile phones have nearly reached saturation among youth, making mobile technology a particularly promising tool to reach this population that has been traditionally hard to reach through clinical services. Smart phone adoption is particularly high among young adults, with approximately 86% of those under age 30 owning a smart phone. Youth are more likely to use their mobile devices for more activities, such as downloading mobile apps, Internet access, social networking, and accessing health

information.^{43,44} The expansion of smart phones has increased the possibilities of dynamic, mobile phone-based HIV prevention interventions.

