5.3 Randomization Procedures

Randomization will be used only for the pilot RCT. Only participants who express interest in using LYNX, meet eligibility criteria, provide informed consent, and complete a baseline assessment will be eligible for randomization. Subjects will be randomized 2:1 into either the LYNX intervention arm (N=40) or control arm (N=20).

The 2:1 allocation will allow us to efficiently gather additional data on app utilization. Randomization will be based on a pre-generated list created by the Analytic Core, with random blocks of size three or six, and stratified by site (Tampa, Chicago) and age (15-18, 19-24). After consent and baseline survey completion, the participant will be randomized (assigned to the next available random allocation). **LYNX Intervention Condition:** Individuals who receive LYNX will be given brief instructions on the purpose of the app, how to access it, and an overview of how to use it. Participants will be encouraged to explore all components of the app and use it routinely. **Standard of Care Condition:** Following screening, participants in both conditions will receive standard of care prevention material consisting of provision of information regarding recommendations for HIV testing and referrals to local HIV testing sites and prevention services.

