6.3.3 On-Study evaluations/measures

- *Acceptability*
 - *System Usability Scale: a validated 10-measure scale that assesses subjective usability of a system, or, in this case, an app. It is scored from 0 to 100, and a score of 50 or greater indicates that the app is acceptable**
 - *In-depth interview (qualitative)*
- *Feasibility: app analytics (frequency of logins, use of LYNX app components)*
 - *We will use app analytics to determine whether at least 60% of individuals randomized to the intervention condition opened the LYNX app at least one time after their initial introduction to the app by research staff**
- *App-Specific Measures*
 - *Frequency and duration of app use*
 - *Content and functionalities most and least utilized*
 - *Number of HIV/STI home testing kits, condoms and lube requested*
- *Preliminary efficacy*
 - *HIV and STI testing frequency*
 - *HIV/STI Testing: participants will be asked to self-report on frequency of HIV/STI testing since last assessment. The primary HIV/STI testing measure will be the proportion of participants who self-report at least one test during the follow up period. We will also explore the concordance of self-report with data collected by medical release and using data electronically self-reported in the app, including home testing kits provided by request through the app.*

- *PrEP interest and uptake*
 - *PrEP care linkage: participants will self-report whether, in the past 3 months, they made and attended a clinic appointment for PrEP initiation, whether they were prescribed PrEP, and whether they utilized PrEP. We will also explore the concordance of self-reported prep use with data on PrEP use collected by medical release.*
- *Sexual and drug use behaviors*
- *Access to and utilization of health care*
- *IMB model constructs for HIV/STI testing and PrEP knowledge, attitudes, motivations, and behavioral skills*
- *Eco-social factors influencing uptake of prevention strategies*
- *Potential moderators of the intervention (measured at baseline and follow-up visits)*
 - *Demographics: Age, student status, education level, income, living situation, employment, insurance status, depressive symptoms, anxiety, trauma, and abuse*

*Primary study endpoints

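### PrEP uptake is planned only on the risk-ratio scale, which gives no estimate if no control has a PrEP event; a risk difference with a score-type interval should be added

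*Combined protocol and SAP*

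**What the plan says.** For the preliminary efficacy outcomes, Section 10.1.3 says that any HIV/STI testing and "PrEP uptake (as described above) will be evaluated using unadjusted risk ratios for each outcome". If measured baseline covariates look unbalanced, "post-hoc analyses using Poisson regression with robust standard errors will be used to estimate adjusted risk ratios". Both steps work on the ratio scale. Chi-square tests are named only for baseline, where the plan will "compare the intervention and control groups at baseline using t-, Wilcoxon, and chi-square tests". No test, interval or risk difference is named for the outcomes, and no rule covers an arm without events.

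The power statement in the same section is on the difference scale: "we will have 80% power to detect 37-42 percentage point increases in HIV testing and PrEP uptake, depending on rates in controls". It allows for a loss of 10-20% of the 60 randomised, and gives neither alpha nor the control rates. Section 5.3 sets the arm sizes ("Subjects will be randomized 2:1 into either the LYNX intervention arm (N=40) or control arm (N=20").

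On the outcome itself, Section 3.0 speaks of comparing the proportions who link to a PrEP provider. Section 6.3.3 lists making and attending an appointment, being prescribed PrEP, and using it. Section 10.2 deals with missing data, not empty cells.

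**The concern.** Participants enter the RCT not taking PrEP (Section 4.1), so every PrEP event in the control arm must arise during follow-up among fewer than 20 people. The background describes low uptake in this population. One cited demonstration study reports that "PrEP uptake was only 16" per cent. With so few controls and a low rate, the control cell can be empty.

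The planned measure then cannot be reported. The only other analysis named, robust Poisson, has no finite solution in that table either, and some software does not say so. Comparing PrEP uptake between arms is a stated secondary objective (Section 2.2), so following the plan as written could leave that objective without an estimate or an interval.

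**Working it through.** **Inputs.** From the documents: 40 v 20 randomised and 10-20% attrition, hence 36 v 18 or 32 v 16 followed (equal loss in both arms assumed); 16% PrEP uptake (Section 1.1); 53% past-year HIV testing (Section 1.1). Assumed: two-sided 5%, and control PrEP rates of 10% and 5% to show the range. The 1.7% ever-use figure in Section 1.1 is a prevalence, so I do not use it as an uptake rate.

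**1. The plan's own power figure.** Pooled two-proportion formula: power = Φ((d − 1.96·SE0)/SE1), with SE0 = √(p̄(1−p̄)(1/n0+1/n1)) and SE1 = √(p0(1−p0)/n0 + p1(1−p1)/n1).
- 36 v 18, control 13%, d = 37 points: p̄ = (18×0.13 + 36×0.50)/54 = 0.377; SE0 = 0.140; SE1 = 0.115; power = Φ((0.37 − 0.274)/0.115) = 0.798. At control 45%, power is 0.795.
- 32 v 16, control 25-30%, d = 42 points: power 0.811-0.813.

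The detectable difference lies within 37-42 points for control rates of 13.0-45.5% (36 v 18) and 7.0-51.5% (32 v 16). The figure reproduces as a two-proportion calculation.

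**2. Chance of an empty control cell.** P = (1 − p)^n.

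| Control PrEP rate | 18 controls | 16 controls |
|---|---|---|
| 16% (Section 1.1) | 0.84^18 = 4% | 0.84^16 = 6% |
| 10% (assumed) | 0.90^18 = 15% | 0.90^16 = 19% |
| 5% (assumed) | 0.95^18 = 40% | 0.95^16 = 44% |

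For HIV testing at 53%, 0.47^16 is below 0.001%. Even at an assumed 30% over six months, 0.70^16 = 0.3%.

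**3. What the planned measures do with 0/18 controls.** The crude ratio divides by zero. In the Poisson model the maximum-likelihood log ratio runs to infinity. Fitting 2/36 v 0/18 with the Python statsmodels GLM routine and robust (HC0) errors reports convergence without warning: ratio about 5×10^8, standard error 0.69, p<0.001. Fisher's exact p is 0.55. The tables 1/36, 4/36 and 14/36 v 0/18 behave the same way. The separate Poisson routine in the same package reports non-convergence for all four tables. What the analyst sees therefore depends on the routine.

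**4. What a risk difference does.** The Newcombe interval combines the two Wilson intervals: lower limit = d − √((p1−l1)² + (u0−p0)²), upper limit = d + √((u1−p1)² + (p0−l0)²). For 2/36 v 0/18, in points, the Wilson intervals are 1.5-18.1 and 0-17.6. The lower limit is 5.6 − √(4.0² + 17.6²) = −12.5, and the upper is 5.6 + 12.6, about 18.1.

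| LYNX v control | Difference (95% CI), points | Chi-square p |
|---|---|---|
| 2/36 v 0/18 | 5.6 (−12.5 to 18.1) | 0.31 |
| 7/36 v 0/18 | 19.4 (−0.6 to 35.0) | 0.045 |
| 14/36 v 0/18 | 38.9 (16.3 to 55.1) | 0.002 |

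**5. Operating characteristics of the addition** (full enumeration of both binomials). Over common rates of 1-70%, type I error is at most 5.4% for chi-square and 5.3% for Newcombe. At the detectable differences (control rates 16-45%), Newcombe coverage is 93.9-95.4% and power is 79-82% for both methods. A plain Wald interval for the difference is not a safe substitute: its exact type I error reaches 8.8% at 36 v 18.

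**The case against.** The strongest reply is that this is a small matter in a pilot. The outcomes are secondary, the primary endpoints (SUS score and opening the app) are untouched, and Section 10.1.3 already asks for careful interpretation. Section 3.0 promises a comparison of proportions, so a reader would see 2/36 against 0/18 and could subtract. At the one uptake figure the documents give, an empty cell has only a 4-6% chance; the larger figures rest on assumed rates. If PrEP uptake is read as the linkage outcome of Sections 3.0 and 6.3.3, events will be more frequent and an empty cell less likely. All of this stands and limits the weight of the point. None of it supplies an estimate with an interval when the planned one does not exist.

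Three stronger readings are tempting, and the documents do not support them.
- A reader might infer that the power sentence is wrong. It is not: step 1 reproduces it. A Wald interval on the log risk ratio would have less power at those differences, but the plan does not name that interval, and a chi-square p-value can accompany a risk ratio because both address the same null.
- A reader might infer that HIV testing is affected too. Step 2 shows that it is not.
- A reader might infer that the plan will produce a spuriously significant Poisson result. That step runs only after baseline imbalance, for which the plan sets no threshold. Some routines flag the failure, and a ratio of several hundred million would probably be noticed.

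It is also fair to say that a chi-square test and a Newcombe interval can disagree in the tables at issue. In 7/36 v 0/18, p is 0.045, the interval includes zero and Fisher's p is 0.08. The remedy must therefore say which one governs.

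**Conclusion.** The point holds for PrEP uptake. The plan's only effect measure for that secondary objective has no value when the control cell is empty, and no fallback is written. The chance is 4-6% at the documents' own 16% and rises to 40-44% at an assumed 5%, given 18 or 16 controls followed. These figures assume equal attrition across arms and that the outcome is starting PrEP; they fall if the outcome is linkage. The consequence is a missing or unreadable secondary estimate, not a threat to the pilot's primary conclusions. It is worth correcting because a better measure is available at almost no cost.

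**What to change.** In Section 10.1.3, for any HIV testing and any PrEP uptake:

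- Report the risk difference with a Newcombe (score-type) 95% confidence interval, and state that this interval governs the description of uncertainty.
- If a p-value is given, use the chi-square test of equal proportions, on which the power sentence appears to rest. Label it supportive, because it can differ from the interval in borderline zero-cell tables.
- Keep the risk ratio as an accompanying measure, and report it as not estimable when the control arm has no events.
- Do not fit the Poisson model when either arm has no events.

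The cost is a few sentences, with no extra data or participants. The downside is one more effect measure to report.
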